9.7.1.8.4 VITAL SIGNS

Descriptive statistics for vital signs parameters (ie, systolic and diastolic BP, pulse, respiratory rate, temperature, weight), and changes from baseline will be presented by visit and treatment group.

9.7.1.8.5 OTHER SAFETY ANALYSES

Cognitive decline will be assessed as a safety assessment, in addition to efficacy assessments. Cognitive assessments will include the ADAS-cog₁₄, MMSE, and CDR. (see [Section 9.7.1.6](#)).

vMRI will be used to evaluate disease modification as indicated by measurements of brain atrophy, including the change from Baseline in terms of the measured hippocampal volume based upon the centralized measurement of the structure on repeated MRIs. A large number of studies, including the AD Neuroimaging Initiative, have shown that quantitative measurements of hippocampal, whole brain, and total ventricular volume provide robust and reliable biomarkers of disease progression, and potential for assessment of PD efficacy.

MRI sequences will be collected for all subjects at 12 and 24 months per the Schedule of Assessments. vMRI data will be analyzed at the Screening Visit and at Visits 9 and 13 (12 and 24 months of treatment). QC and normalization procedures for measurements of the whole brain, total ventricular volume, and right and left hippocampal volumes will be based on a validated algorithm and conducted in the same central laboratory. Additional analysis of regions of interest and cortical thickness may also be performed.

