9.7.1.6.1 PRIMARY EFFICACY ANALYSIS

The primary analysis will be based on an intent to treat philosophy without regard to adherence to treatment. The primary analysis of the change from baseline in CDR-SB at 24 months will be performed to compare elenbecestat (E2609) 50 mg per day versus placebo using a linear mixed effects model for repeated measures (MMRM) on the FAS. The MMRM model will include baseline CDR-SB as a covariate, with treatment group, visit, randomization stratification variables (ie, region [7 levels], clinical dementia [yes, no], and concurrent AD medication use at randomization (Visit 2) [yes, no]), and treatment group-by-visit interaction as fixed effects. (revised per Amendments 01 and 02) An unstructured covariance matrix will be employed to model the covariance of within subject effect; if MMRM fails to converge then a covariance structure with fewer parameters from the following list will be employed according to the prespecified order in the list until the MMRM converges. The list of covariance structure will include Heterogeneous Toeplitz, Toeplitz, Heterogeneous Compound Symmetry, and Compound Symmetry. This primary analysis will include all observed post baseline data of the change from baseline in CDR-SB without imputation of missing values. The treatment effect for elenbecestat (E2609) versus placebo will be compared at 24 months based on MMRM model. The LS means and difference in LS means between elenbecestat (E2609) treatment group and placebo, and corresponding 95% CI will be presented.

The null hypothesis is that there is no difference in the mean change from baseline in CDR-SB at 24 months between elenbecestat (E2609) 50 mg per day and placebo. The corresponding alternative hypothesis is that there is a difference in the mean change from baseline in CDR-SB at 24 months between elenbecestat (E2609) 50 mg per day and placebo.

The primary analysis will be repeated to minimize the impact of change in concomitant AD medications where efficacy data after initiation of new AD medications and increase of current AD medications will be censored.

The following sensitivity analysis will be conducted to evaluate the impact of missing data: the primary endpoint will be analyzed using ANCOVA after multiple imputation. The ANCOVA model will include baseline CDR-SB as a covariate, with treatment group and randomization stratification variables as factors.

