9.7.1.8 Safety Analyses

Evaluations of safety will be performed on the Safety Analysis Set. The incidence of AEs, out-of-normal-range laboratory safety test variables, abnormal ECG findings, and out-of-range vital signs, suicidality, results of the sleep questionnaire, along with change from baseline in laboratory safety test variables, ECGs, and vital sign measurements will be summarized by treatment group. (revised per Amendment 01)

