^b Subjects who discontinue taking study drug prematurely for any reason will undergo an ED Visit within 7 days of their last dose of study drug. In addition, Follow-Up Visits will be scheduled 4 and 12 weeks after the last dose of study drug (Visit 14 and Visit 15, respectively). Subjects who discontinue study drug before reaching 12 months of treatment will also be asked to return to the clinic for a 12 month clinical assessment and then again at 24 months. Subjects who discontinue treatment between 12 and 24 months of treatment will be asked to return to the clinic for a 24 month clinical assessment. Subjects who discontinue early from study drug are considered “on study” as long as they continue to return for their clinical assessments at 12 and 24 months as outlined above, at which efficacy (MMSE, CDR, ADAS- cog₁₄) and quality of life (EQ-5D, QOL-AD and Zarit’s Burden Interview) will be assessed along with concomitant medications and AEs. These 12 and 24 month clinical assessment visits do not need to be attended if they fall within 8 days (visit window) after the ED Visit or within ±8 days of either of the Follow-Up Visits (Visit 14 and Visit 15).

- ^c All subjects, regardless of whether they complete all 24 months of treatment or discontinue study drug prematurely, will complete 2 posttreatment Follow-Up Visits; one 4 weeks after the last dose of study drug and a second 12 weeks after the last dose of study drug (Visit 14 and Visit 15 respectively). If clinically indicated, more frequent safety assessments can be made as UNS assessments or visits during the posttreatment Follow-Up Period. Subjects who have a Grade 2 or greater lymphocytopenia (less than 800/mm³) during the follow-up period (ie., at either Visit 14 or Visit 15) should have ALC measured every 4 weeks until resolution or confirmation of a non drug-related cause of the lymphocytopenia. ALC will be derived from the complete blood count (CBC) with differential representing the normal lymphocytes (with atypical lymphocytes removed and presented as a separate count if they are present) and calculated by the white blood cell count × percentage of lymphocytes. (revised per Amendments 01 and 02) (revised per Amendments 01 and 02)

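### The one comparison of the cognitive scales that 9.7.1.8.5 points to for safety is the intent-to-treat efficacy analysis, which suits a harm question poorly: wrong analysis set, off-drug values included, and two scales conditional on a significant primary result.

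*Protocol*

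**What the plan says.** Section 9.7.1.8.5 (Other Safety Analyses) names cognitive decline as a safety outcome: "Cognitive decline will be assessed as a safety assessment, in addition to efficacy assessments". It then lists the instruments: "Cognitive assessments will include the ADAS-cog₁₄, MMSE, and CDR". It gives no analysis of its own for them and ends in a bracketed reference to Section 9.7.1.6, the efficacy analyses. The parent section, 9.7.1.8, states: "Evaluations of safety will be performed on the Safety Analysis Set".

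Section 9.7.1.6 takes the FAS as its main population and the PPS as supportive. For CDR-SB, Section 9.7.1.6.1 says: "The primary analysis will be based on an intent to treat philosophy without regard to adherence to treatment". It adds: "This primary analysis will include all observed post baseline data of the change from baseline in CDR-SB without imputation of missing values". The treatment effect "will be compared at 24 months based on MMRM model". Section 9.7.1.6.2 makes the secondary analyses, which include ADAS-cog14 and MMSE at 24 months, conditional on a significant primary result.

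Under Table 4, footnote b, subjects who stop drug before month 12 "will also be asked to return to the clinic for a 12 month clinical assessment and then again at 24 months"; those who stop later are asked back at month 24. CDR, MMSE and ADAS-cog14 are measured at these visits. The scales are also given at the Early Discontinuation (ED) Visit, due within 7 days of the last dose.

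**The concern.** Off-drug values are the cautious choice when the question is benefit. When the question is harm they can work the other way. If the drug worsens cognition and the effect recovers after stopping, the values of returned stoppers move the month 24 difference towards zero. The score taken closest to treatment, at the ED Visit, is generally not a month 24 value, and no on-treatment summary of the scales is stated. Laboratory values do have one: Section 9.7.1.8.3 defines end of treatment as the last on-treatment value.

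Two further problems need no assumption about reversal. The reference takes a safety outcome to the FAS although the parent section specifies the Safety Analysis Set. And if 9.7.1.6.2 is followed literally, a non-significant primary result would leave ADAS-cog14 and MMSE with no comparison between arms. That is an outcome in which one would want to know whether the drug made cognition worse.

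At stake is a modest average worsening that an investigator could not distinguish from disease progression in one subject, in a population assumed to worsen by 1.75 points on placebo.

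**Working it through.** **Set and gating, by reading.** 9.7.1.8 specifies the Safety Analysis Set, which requires one dose and one postdose safety assessment. 9.7.1.6 specifies the FAS, which requires one dose, a baseline and one postdose primary efficacy measurement. 9.7.1.8.5 sits under the first and refers to the second without saying which governs. The gate in 9.7.1.6.2 has no exception for use of the same scales as safety outcomes.

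**The plan's own figure.** Inputs from 9.7.2: placebo mean change 1.75, SD 2.05, 25% reduction, 30% dropout, 90% power, two-sided alpha 0.05, 665 per arm.
- Difference = 0.25 × 1.75 = 0.4375.
- n per arm = 2 × (1.960 + 1.282)² × 2.05² / 0.4375² ≈ 462.
- Divided by 0.70: 660 per arm (about 662 with the t distribution), against 665 stated. The figure reproduces.
- Power with 665 × 0.70 = 465.5 per arm: 0.902.

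**Attenuation of a reversible harm.** Assumptions that are not in the documents: an on-drug worsening of 0.30 CDR-SB points at month 24; the planned 30% dropout read as stopping drug, equally in both arms; and a fraction f of all randomised subjects (0.10, 0.20 or 0.30) with an off-drug month 24 value. Let r be the share of the harm that reverses off drug.
- Intent-to-treat difference = 0.30 × (0.70 + (1 − r) × f) / (0.70 + f).
- SE = 2.05 × √(2 / (665 × (0.70 + f))).
- On-treatment: difference 0.30, SE = 2.05 × √(2 / 465.5) = 0.134, power 0.607.

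| r | f = 0.10 | f = 0.20 | f = 0.30 |
|---|---|---|---|
| 1 (full): difference, power | 0.263, 0.551 | 0.233, 0.504 | 0.210, 0.463 |
| 0.5 (half): difference, power | 0.281, 0.609 | 0.267, 0.614 | 0.255, 0.621 |

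Under full reversal the shrinkage is f / (0.70 + f): 12.5%, 22.2% and 30%. At half reversal the estimate is 6% to 15% smaller, but the extra observations offset this and power is no lower than the on-treatment 0.607. With no reversal nothing is diluted.

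**Same check at 0.4375.** With full reversal and every stopper returning (f = 0.30), the difference is 0.4375 × 0.70 = 0.306 and power falls from 0.90 to 0.78. At half reversal it is 0.4375 × 0.85 = 0.372 with power 0.91, so detection is not reduced.

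**The case against.** A reader might infer that the month 24 intent-to-treat contrast is the only group comparison planned for cognitive harm. The documents do not support that. Section 9.5.1.5.1 has decline during the Treatment Period reported as an adverse event when the investigator judges it excessive. Section 9.5.1.5.5 lists cognitive decline beyond expectation among the neurologic signs that may need investigation, and has abnormal treatment-emergent neurologic findings reported as adverse events. Section 9.7.1.8.2 tabulates treatment-emergent events by arm on the Safety Analysis Set. Nor is 9.7.1.6 a single contrast. Its model has treatment-by-visit terms with CDR every 3 months, and 9.7.1.6.2 adds a CDR-SB slope and times to CDR worsening and to dementia. A confirmed worsening before stopping still counts in the CDR time-to-event analysis. These points stand, with two limits: the adverse event route depends on case-by-case judgement, and the 9.7.1.6.2 analyses are all gated on the primary result.

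A reader might also infer that an on-treatment comparison is always the more sensitive one. It is not, as the half-reversal row shows. If harm itself causes stopping, an on-treatment comparison loses the harmed subjects at later visits and can also drift towards zero.

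The bracketed reference can be read as merely locating the efficacy results, with 9.7.1.8 still governing the set, and an SAP that is not shown may add an on-treatment display. That is fair, and it is why this is a minor point. But the protocol does name a method here, and read as written it conflicts on the analysis set and carries the gate.

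**Conclusion.** The point holds as a minor one. For comparing the cognitive scales between arms as safety outcomes, 9.7.1.8.5 states only a reference to an analysis built for benefit. Two defects follow from the text alone: the FAS in place of the Safety Analysis Set, and the dependence of ADAS-cog14 and MMSE on a significant primary result. The third, attenuation by off-drug values, is conditional. It is about 12% to 30% of the month 24 difference under full reversal with 10% to 30% of subjects giving off-drug values, 6% to 15% at half reversal, and nil without reversal. Power suffers only when more than about half of the harm reverses. Reversal, return rates and the 0.30-point effect are assumptions, and the 30% in 9.7.2 is a dropout rate, not a stated rate of stopping drug. Scheduled off-drug returns occur only at months 12 and 24, apart from the follow-up visits after the last dose. No figure in the protocol is wrong, and the primary efficacy analysis is not in question.

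**What to change.** In 9.7.1.8.5, replace the bare reference with wording to this effect: *Regardless of the result of the primary analysis, change from baseline in CDR-SB, ADAS-cog14 and MMSE will be summarised and compared between arms by visit, with 95% CIs, on the Safety Analysis Set, using assessments up to 7 days after the last dose, with the Early Discontinuation Visit assigned to its actual month. The intent-to-treat results of Section 9.7.1.6 will be shown alongside.*

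The cost is this wording and one further model run per scale. The data are already collected and the primary analysis does not change. The downside is selection: an on-treatment comparison depends on who stops and may lose harmed subjects at later visits. Early visits and the intent-to-treat result must therefore be read together with it.

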9.7.2 Determination of Sample Size

The sample size for this study is estimated based on comparison of elenbecestat (E2609) versus placebo with respect to the primary efficacy endpoint, the change from baseline CDR-SB at 24 months. Based on available ADNI data [amyloid positive, MMSE equal or greater than 24, late MCI (global CDR=0.5) populations from ADNI, ADNI 2 and ADNI GO] the mean and the standard deviation of the change from baseline in the CDR-SB at 24 months in the placebo group are assumed to be 1.75 and 2.05, respectively. Therefore, assuming a 25% reduction in the mean change from baseline CDR-SB at 24 months for the elenbecestat

(E2609) 50 mg per day dose group compared to placebo with a common standard deviation of 2.05 and an estimated 30% dropout rate in this study, a total sample size of 1330 subjects, 665 subjects in each treatment group, will be required to detect the treatment difference between elenbecestat (E2609) 50 mg per day and placebo using a 2-sample t-test with 90% power at a significance level of 2-sided alpha =0.05.

9.7.3 Interim Analysis

This is a fixed design. There is no interim analysis of efficacy and no alpha spending before final analysis. However, a futility analysis is planned when 30% subjects have completed 24 months. The sponsor may stop the trial for futility with nonbinding futility boundary calculated using conservative O'Brien-Fleming boundary of Lan-DeMets alpha spending function with 30% information based on completers. If the actual percent information of the futility analysis is different from 30%, the futility boundary will be recalculated using the actual percent information at time of futility analysis. A blinded sample size re-estimation through estimated standard deviation based on blinded data prior to the completion of enrollment, will be performed if there is an indication that sample size assumptions need to be changed. This blinded sample size re-estimation could be performed based on signals from external studies or based on review of blinded data from this study prior to completion of enrollment. The standard deviation of the primary endpoint was estimated based on data from the ADNI study. It is possible that the standard deviation for the same endpoint in clinical trials may be larger than that from this observation study.

An independent DSMB will convene at regular intervals to monitor the overall safety of the study and to make recommendations to the sponsor related to study safety as appropriate. The DSMB will be asked to review the cumulative safety data up to the date identified to make a determination if the trial is safe to proceed unchanged or to provide recommendations to the Sponsor as to how to proceed. The study will proceed, including randomization of additional subjects, during DSMB safety reviews. DSMB reviews will then continue to occur at regular intervals. Details will be provided in the DSMB Charter.

9.7.4 Other Statistical/Analytical Issues

Not applicable.

9.7.5 Procedure for Revising the Statistical Analysis Plan

If the statistical analysis plan needs to be revised after the study starts, the sponsor will determine how the revision impacts the study and how the revision should be implemented. The details of the revision will be documented and described in the clinical study report.

11 PROCEDURES AND INSTRUCTIONS (ADMINISTRATIVE PROCEDURES)

11.1 Changes to the Protocol

Any change to the protocol requires a written protocol amendment or administrative change that must be approved by the sponsor before implementation. Amendments specifically affecting the safety of subjects, the scope of the investigation, or the scientific quality of the study require submission to health or regulatory authorities as well as additional approval by the applicable IRBs/IECs. These requirements should in no way prevent any immediate action from being taken by the investigator, or by the sponsor, in the interest of preserving the safety of all subjects included in the study. If the investigator determines that an immediate change to or deviation from the protocol is necessary for safety reasons to eliminate an immediate hazard to the subjects, the sponsor's medical monitor and the IRB/IEC for the site must be notified immediately. The sponsor must notify the health or regulatory authority as required per local regulations.

Protocol amendments that affect only administrative aspects of the study may not require submission to health or regulatory authority or the IRB/IEC, but the health or regulatory authority and IRB/IEC (or if regionally required the head of the medical institution) should be kept informed of such changes as required by local regulations. In these cases, the sponsor may be required to send a letter to the IRB/IEC and the Competent Authorities (or, if regionally required, the head of the medical institution) detailing such changes.

11.2 Adherence to the Protocol

The investigator will conduct the study in strict accordance with the protocol (refer to ICH E6, Section 4.5).

11.3 Monitoring Procedures

The sponsor's or CRO's CRA will maintain contact with the investigator and designated staff by telephone, letter, or email between study visits. Monitoring visits to each site, and potential remote source document verification, will be conducted by the assigned CRA as described in the monitoring plan. The investigator (or if regionally required, the head of the medical institution) will allow the CRA to inspect the clinical, laboratory, and pharmacy facilities to assure compliance with GCP and local regulatory requirements. The eCRFs and subject's corresponding original medical records (source documents) are to be fully available for review by the sponsor's representatives at regular intervals. These reviews verify adherence to study protocol and data accuracy in accordance with local regulations. All records at the site are subject to inspection by the local auditing agency and to IRB/IEC review.

In accordance with ICH E6, Section 1.52, source documents include, but are not limited to, the following:

- Clinic, office, or hospital charts
- Copies or transcribed health care provider notes that have been certified for accuracy after production
- Recorded data from automated instruments such as IxRS, x-rays, and other imaging reports (eg, sonograms, computed tomography scans, MRIs, radioactive images, ECGs, rhythm strips, electroencephalography, polysomnographs, pulmonary function tests) regardless of how these images are stored, including microfiche and photographic negatives
- Pain, quality of life, or medical history questionnaires completed by subjects
- Records of telephone contacts
- Diaries or evaluation checklists
- Drug distribution and accountability logs maintained in pharmacies or by research personnel
- Laboratory results and other laboratory test outputs (eg, urine pregnancy test result documentation and urine dip-stick test result documentation)
- Correspondence regarding a study subject's treatment between physicians or memoranda sent to the IRBs/IECs
- CRF components (eg, questionnaires) that are completed directly by subjects and serve as their own source.

11.4 Recording of Data

A CRF is required and must be completed for each subject by qualified and authorized personnel. All data on the CRF must reflect the corresponding source document, except when a section of the CRF itself is used as the source document. Any correction to entries made on the CRF must be documented in a valid audit trail where the correction is dated, the individual making the correction is identified, the reason for the change is stated, and the original data are not obscured. Only data required by the protocol for the purposes of the study should be collected.

The investigator must sign each CRF. The investigator will report the CRFs to the sponsor and retain a copy of the CRFs.

11.5 Identification of Source Data

All data to be recorded on the eCRF must reflect the corresponding source documents, except when a section of the CRF itself is used as the source document.

11.6 Retention of Records

The circumstances of completion or termination of the study notwithstanding, the investigator (or if regionally required, the head of the medical institution or the designated representative) is responsible for retaining all study documents, including but not limited to the protocol, copies of eCRFs, the Investigator's Brochure, and regulatory agency registration documents (eg, Form FDA 1572, ICFs, and IRB/IEC correspondence). The site should plan to retain study documents, as directed by the sponsor, for at least 2 years after the last approval of a marketing application in an ICH region and until there are no pending or contemplated marketing applications in an ICH region or at least 3 years have elapsed since the formal discontinuation of clinical development of the investigational product.

It is requested that at the completion of the required retention period, or should the investigator retire or relocate, the investigator contact the sponsor, allowing the sponsor the option of permanently retaining the study records.

